3.2 Study description

Pre-assessment by the GP or delegate (gauging interest, with general in- and exclusion criteria in mind) will preferable be done face-to face, and only remote if circumstances demand and approvals in place (see section 4.1 Population). After having fully informed the potential participant the informed consent procedure will be executed. There will be a person-to-person discussion about the trial when taking consent with all participants, and there will be an opportunity for asking questions and for full verbal explanations. This conversation may be face to face or video call (see chapter 11). After obtaining IC, eligibility for trial participation will be checked (general and specific in- and exclusion criteria). Eligible participants will be randomly allocated to receive either an IP or a control. Each IP and control will have its own appendix. The aim is for randomisation and IP initiation to occur within 7 days of symptom onset; some IPs may require a faster initiation which will be specified in its ISA. Baseline information will be collected (see section 8.3 Study Procedures). Participants will receive study instructions, including how to administer the IP/control product (if participant is allocated to a study arm with an IP or control product). IP and control treatment duration will be described in the ISAs. Use of diaries and questionnaires will be explained. These diaries and questionnaires can be online, paper-based, or completed by telephone, and the relevant and preferred approach will be explained, and access provided.

Participants will be asked to report feeling recovered, individual respiratory symptoms, overall wellbeing, AEs, use of mediation, complications, impact on usual daily activity and health care utilisation in a daily diary (either paper or online) for 28 days following randomisation.

A swab will be (self)-taken at baseline (day 0, this swab will be also used to determine disease aetiology (retrospectively)) and subsequently on day 4, 7 and 14; if additional swabs are needed then this will be specified in the ISA. Blood samples or blood spot tests (self)-taken may be taken at inclusion and later, if specified in the ISA.

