| Blood sample | | | If required, see ISA | | | |
| Long-term infection consequences | | | | | х | х |
| Interview for qualitative study (if invited) | | Approximately two weeks after the initial consultation | | | | |
| (S)AEs, if required see ISA | х | Daily | x | х | | |

¹ Virology sample will be taken on day 0, 4, 7 and 14 (if additional swabs are needed then this will be specified in the ISA) ² If inclusion is face-to-face

³ The duration of study product intake is dependent on the IP requirements and can start on Day 0 or Day 1.

⁴ In case data capture is not complete

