9.2 AEs, SAEs and SUSARs

9.2.1 Adverse events (AEs)

AEs will be recorded for a maximum of 28 days. AEs are defined as any undesirable experience, unrelated to the respiratory infection, occurring to a participant during the study, whether or not considered related to the IP. For each IP/control, all AEs reported by participants in a daily diary from the start of treatment for a 28-day period or during the end-of-treatment telephone call assessment at day 14 (window 14-18 days) after randomisation) will be recorded. AEs will be assessed by a registered/delegated clinician for causality and severity (definitions below).

The participant will be asked to rate the severity of symptoms related to the respiratory infection, which can also be adverse drug reactions (for example headache), in their daily diary. The severity of individual events and symptoms will be assessed over time by participants on the following scale: absent, mild, moderate, severe.

Respiratory symptoms and adverse drug reactions may overlap and can be difficult to disentangle. Trends in the prevalence in the severity of symptoms between control and IP arms will be compared, for evidence of increased severity of measured symptoms in those randomised to receive IPs.

Participants will be free to withdraw from taking the IP/control if they perceive an intolerable AE, unrelated to the respiratory infection. Participants will be provided with a participant card with a telephone number of the coordinating team, enabling them to report issues that are experienced whilst taking the drug. This card will also alert hospital clinicians about trial participation, should a participant be admitted to hospital. In the event of a medical emergency, trial participants will be instructed to show this card to the clinician they see. Based on clinical judgement, the medical monitor/study team may contact the participant to advise the participant on the appropriate clinical care.

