10.1 Primary study estimand and parameter(s)

10.1.1 Definition of the primary estimand

Participants aged ≥18 years with at least 2 symptoms suggestive of COVID-19 or COVID-likeillness (one respiratory and one systemic) and meeting the IP eligibility criteria, what is the between group difference, estimated by a hazards ratio, in time to first self-report of feeling recovered (TTR) after treatment with an IP compared with placebo or comparator, regardless of treatment discontinuation for any reason or feeling better before starting the medication, and in conjunction with concomitant medication (including anti-viral medication) as necessary? Participants who die within 28 days from randomisation will be censored at 28 days. TTR is measured by response to the daily diary question "do you feel recovered today from your respiratory infection?", and censored at 28 days after randomisation.

Attributes of estimand:

Population – people in the community aged ≥18 years with at least 2 symptoms suggestive of COVID-19 or COVID-like-illness (one respiratory and one systemic) and meeting the IP eligibility criteria.

Treatment conditions – IP compared with placebo or comparator, regardless of treatment discontinuation for any reason or feeling better before starting the medication, and in conjunction with concomitant medication (including anti-viral medication) as necessary. Participants who die will be given a worst-case value and censored at 28 days.

Outcome variable – time to first self-report of feeling recovered, as measured by response to the daily diary question "do you feel recovered today from your respiratory infection?", censored at 28 days after randomisation.

Handling of intercurrent events – treatment policy strategy applied to study treatment discontinuation, feeling better before starting the medication and use of concomitant medication (including anti-viral medication). Composite strategy applied to death within 28 days of randomisation.

Population level summary measure – hazard ratio.

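### Section 9.2.1 counts diary AEs from the start of treatment, contradicting the randomisation-based window used elsewhere and leaving Usual Care without a start date

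*Protocol*

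**What the plan says.** Section 9.2.1 gives the AE recording rule. It opens with a cap, "AEs will be recorded for a maximum of 28 days", without saying from when the 28 days run. It then names two routes. The first is the diary: "all AEs reported by participants in a daily diary from the start of treatment for a 28-day period". The second is the call made "during the end-of-treatment telephone call assessment at day 14 (window 14-18 days) after randomisation". The rule covers control arms too, since it begins "For each IP/control, all AEs reported by participants in a daily diary".

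Other sections count from randomisation. Section 3.2 has participants report "individual respiratory symptoms, overall wellbeing, AEs, use of mediation, complications" and other items "in a daily diary (either paper or online) for 28 days following randomisation". Section 8.3.2 lists AEs among the daily diary items for the 28 days. The (S)AE row of Table 1 is marked at Day 0, daily on Days 1-28 and at both telephone calls, with no split by arm. Section 8.2.1 defines Day 0 as the day of randomisation.

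On when product begins, footnote 3 of Table 1 says: "The duration of study product intake is dependent on the IP requirements and can start on Day 0 or Day 1". The estimand in section 10.1.1 applies "regardless of treatment discontinuation for any reason or feeling better before starting the medication", so it foresees that some people may improve before first use. The synopsis describes Usual Care as an arm without study product and makes it the comparator of Saline.

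**The concern.** A window that opens at the start of treatment can only be applied to someone who starts a treatment. One of the three opening arms, allocated 1:1:1, has none, and the protocol defines no substitute date for it. Participants allocated a spray who never use it are in the same position.

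Section 10 tabulates AEs by treatment arm. If a site or coordinating team follows 9.2.1 to the letter, diary events before first use, and diary events in people who never start, would be left out in the Saline arm. In Usual Care, events would be counted from randomisation or would fall under no diary rule at all. Part of any difference between those two columns could then come from the recording rule and not from the spray. This comparison is also not blinded (section 8.2.3), so the recording rule should be the same on both sides. It is a collection rule, and an event left unrecorded cannot be restored in the analysis.

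**Working it through.** The protocol gives no figure to reproduce. The check sets the anchors side by side and then does calendar-day arithmetic.

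**Step 1. Anchors for the same data**

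| Place | Counted from | Applies to |
|---|---|---|
| 9.2.1, diary | start of treatment, 28 days | each product and control |
| 9.2.1, cap | 28 days, no origin given | not stated |
| 9.2.1, day 14 call | randomisation | all (section 3.2) |
| 3.2, diary | randomisation, 28 days | all |
| Table 1, (S)AE row | Day 0, then Days 1-28 | all, no split by arm |

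Only the diary part of 9.2.1 counts from the start of treatment.

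**Step 2. Window by start day**

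Let s be the day of first product use. Counting that day as the first of 28, the 9.2.1 window is Day s to Day s + 27. The diary ends on Day 28, so the days covered are min(28, s + 27) − s + 1.

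- s = 0: 27 − 0 + 1 = 28 of 28 (Days 0-27).
- s = 1: 28 − 1 + 1 = 28 of 28 (Days 1-28).
- s = 2 (assumed): 28 − 2 + 1 = 27 of 28.
- s = 3 (assumed): 28 − 3 + 1 = 26 of 28.
- s = 7 (assumed): 28 − 7 + 1 = 22 of 28.

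If the period is read as the start day plus 28 further days, s = 0 ends on Day 28 and s = 1 ends on Day 29, one day after the diary closes. Under either reading, the days from Day 0 that precede the window number s: none for a Day 0 start and one for a Day 1 start. For the two start days that the protocol names, the shift is therefore at most about one day. Starts after Day 1 are an assumption, because no distribution of start days is given.

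**Step 3. Participants without a start day**

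For Usual Care and for never-starters, s does not exist. The diary part of 9.2.1 gives them no window, while Table 1 gives them Days 0-28.

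**Step 4. Comparisons touched**

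- NONS versus Saline: both arms have s, under the same rule and with blinding. No systematic difference is expected.
- Saline versus Usual Care: one side has s and the other does not. The mismatch lies here.

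**Step 5. With randomisation as the anchor**

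Every participant has Day 0 to Day 28, as Table 1 already schedules.

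**The case against.** The strongest reply is that this is a slip of wording in one sentence. The diary, Table 1 and the calls already cover randomisation to day 28 in all arms, and section 9 adds visits, medical records and spontaneous reports. That stands in part. The protocol does not consistently prescribe different windows; it contradicts itself. A reader might infer that events are actually lost from the product arms, but the documents do not show this.

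A reader might also infer that every Usual Care event, or every event in a never-starter, falls outside any window. That goes too far even on the text of 9.2.1, because the day 14 call is counted from randomisation and section 3.2 gives it to all participants.

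A loss proportional to the delay before first use is equally unsupported. Day 0 and Day 1 starts still fit 28 days into the diary. Section 8.2.1 mentions couriered product for centrally recruited participants, and sections 4.1 and 4.1.3 allow central recruitment only under an approved amendment.

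Two further points narrow the matter. The sentence in 9.2.1 about comparing control and product arms concerns the severity of diary symptoms, not AE counts. The Safety Analysis Set in section 10.6 is limited to people who used the product at least once, so never-starters cannot distort an analysis in that set. However, section 10 does not name the set for its AE table by arm. Whether that set suits Usual Care at all is a separate question.

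Finally, each product and control has its own appendix, and the (S)AE row of Table 1 refers to it. Those appendices may settle the anchor. Even so, the master rule would still contradict its own schedule, and later arms follow the master protocol by default.

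**Conclusion.** The point holds as an internal contradiction with one practical consequence. The diary rule in 9.2.1 conflicts with 3.2, 8.3.2 and Table 1 on when AE recording begins, and it cannot be applied to Usual Care or to participants who never start product. Read literally, Saline and Usual Care do not share one AE window.

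The size is small where it can be worked out: at most about one day for Day 0 or Day 1 starts. For later starts and never-starters it cannot be worked out, because the protocol gives neither their number nor their timing. NONS versus Saline is not systematically affected.

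This rests on the protocol alone, with the intervention appendices unseen, and on counting the start day as the first of the 28. It should be corrected, because a stated collection rule fails for one of three arms in an open-label comparison and the correction is easy.

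**What to change.** In 9.2.1, replace the start-of-treatment anchor with a single AE recording window: randomisation (Day 0) to day 28 in every arm, including Usual Care and participants who never start product. Give the 28-day cap in the same sentence the same origin, and word it as ending on day 28, since Day 0 to Day 28 touches 29 calendar dates. Check that 3.2, 8.3.2, Table 1 and the intervention appendices say the same.

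Keep on-treatment status as a separate flag, derived from the date of first product use in the intake diary (section 7 and the intake row of Table 1).

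The cost is about one sentence plus a consistency check. The diary and calls already cover these days in all arms, so no visit, call or diary item is added.

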10. STATISTICAL ANALYSIS

Full details of the statistical analysis will be described in the Master Statistical Analysis Plan (M-SAP). An appendix to the M-SAP titled "Simulation Report" provides simulation results that justify the sample size and design of the study. In addition, the M-SAP will be accompanied by arm-specific appendices to describe any planned deviations from the M-SAP. A broad overview of the design and primary analysis is provided below.

ECRAID-Prime is an adaptive platform trial with early stopping rules for futility or superiority. Comparisons will be based on concurrent and eligible controls only, where control is either a (matched) placebo or comparator, or, if deemed necessary, Usual Care. If there are 2 matched placebos with concurrent randomisation, the primary analysis will pool controls unless it is decided otherwise and specified in the ISA. We may carry out sensitivity analyses with matched controls only included. Early stopping rules will be based on posterior probabilities with thresholds defined using simulations to ensure good trial performance with respect to power and type 1 error.

Each treatment will be analysed separately.

Baseline characteristics will be summarised by IP arm. Continuous variables will be presented as means and standard deviations (or medians and inter-quartile ranges for skewed data). Categorical and binary data will be presented as frequencies and percentages. AEs and SAEs will be summarised by treatment arm.

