10.6 Definition of population for analysis

For each intervention, the primary analysis population is defined as participants who were randomised to that intervention or the usual care arm and eligible for randomisation to that intervention, during the same time frame when the intervention was actively randomising (i.e. Concurrent Randomised and Eligible Analysis Population) and have at least one post-baseline measurement.

Primary Analysis Set:

For each IP, all participants randomised to either the IP or its comparator (placebo or usual care and eligible for the IP). Participants later found to be ineligible (randomised in error) will be excluded. Non-concurrent comparators will not be included.

Safety Analysis Set:

All participants who took at least one dose of IP.

Symptomatic Analysis Set:

Primary Analysis Set restricted to those participants who report having the symptom at baseline.

Symptom Free Analysis Set:

Primary Analysis Set restricted to those participants who report not having the symptom at baseline.

Virology Analysis Set:

To be defined

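### For symptoms shared with the illness, the symptom comparison in section 9.2.1 measures drug-caused harm net of faster recovery, so it can understate harm for an effective product

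*Protocol*

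**What the plan says.** Section 9.2.1 defines AEs so as to leave out the illness: "AEs are defined as any undesirable experience, unrelated to the respiratory infection, occurring to a participant during the study". Diary symptoms are rated separately by the participant: "The severity of individual events and symptoms will be assessed over time by participants on the following scale: absent, mild, moderate, severe". The section gives headache as an example of a symptom that may be a drug reaction, and concedes the difficulty: "Respiratory symptoms and adverse drug reactions may overlap and can be difficult to disentangle". Its answer is a single sentence: "Trends in the prevalence in the severity of symptoms between control and IP arms will be compared, for evidence of increased severity" among those randomised to an IP. That sentence sets no limit to new onset, to worsening from day 0, to the days of product use, or to participants without the symptom at the start.

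Two other places bear on this. AEs have their own route: "AEs will be assessed by a registered/delegated clinician for causality and severity" (9.2.1) and "AEs and SAEs will be summarised by treatment arm" (section 10). Section 10.6 defines a Symptom Free Analysis Set, "Primary Analysis Set restricted to those participants who report not having the symptom at baseline", and a matching Symptomatic Analysis Set. Neither is linked to the comparison in 9.2.1.

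**The concern.** Take a symptom that is part of the illness and can also be caused by the product. Section 8.1.2 lists several candidates, among them headache, fatigue, nausea or vomiting, sore throat and a runny or congested nose. A plain between-arm comparison of such a symptom adds two effects of opposite sign. The product may cause the symptom, and if it works it also clears the illness version sooner. The platform exists to find products with the second effect, so the harm check is weakest for the products most likely to succeed.

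The AE route does not fully close the gap. A drug-caused headache enters it only if someone first judges the headache to be unrelated to the infection, which is the judgement the section calls difficult. At stake is a statement that symptoms were no more severe on the IP, made for a product that does cause symptoms.

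**Working it through.** The protocol gives no figure on this point and leaves sample size to the intervention appendices (section 4.4). Every input below is therefore assumed. Both models treat a symptom as present or absent and ignore its grade. HR is the hazard ratio for resolution of that symptom.

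**Check 1: how much harm is masked exactly?** A share b has the symptom at day 0, and it resolves exponentially with median m days in control. On the IP the resolution hazard is multiplied by HR, and the product causes the symptom on any of days 1-7 with probability p.

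- Control prevalence on day d: S_C = b × 2^(−d/m)
- Illness prevalence on the IP: S_IP = b × 2^(−HR×d/m)
- Observed prevalence on the IP: S_IP + (1 − S_IP) × p
- No net excess when p* = (S_C − S_IP)/(1 − S_IP)

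Worked case, day 4, b = 0.5, m = 7, HR = 1.3: S_C = 0.3365, S_IP = 0.2988, p* = 0.0377/0.7012 = 0.054.

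Break-even p* from the mean prevalences over days 1-7:

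| b | m (days) | HR 1.2 | HR 1.3 | HR 1.5 |
|---|---|---|---|---|
| 0.5 | 4 | 3.7% | 5.3% | 8.0% |
| 0.5 | 7 | 3.4% | 5.0% | 7.7% |
| 0.8 | 4 | 7.3% | 10.2% | 15.0% |
| 0.8 | 7 | 7.7% | 10.9% | 16.3% |

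At HR 1.0 nothing is masked. With p = 5%, b = 0.8 and m = 7, the mean net difference over days 1-7 is +2.3 points at HR 1.0, −1.3 at HR 1.2 and −3.0 at HR 1.3. The same harm therefore changes from a visible excess to an apparent benefit.

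**Check 2: power of three contrasts.** The simulation assumes 300 per arm, the symptom in 60% at day 0, a resolution hazard of 0.15 per day, natural onset of 3% per day for 4 days, and a drug-caused symptom on days 1-7 in 15% of users. The test is a two-sample z at two-sided 0.05, counting only the harm direction.

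| Contrast | Power, HR 1.0 | Power, HR 1.25 | Difference, HR 1.25 |
|---|---|---|---|
| Mean prevalence, days 1-28, all | 28% | 1% | −0.5 points |
| Mean prevalence, days 1-7, all | 77% | 39% | +5.8 points |
| New onset, days 1-7, symptom-free at day 0 | 76% | 77% | +13.3 points |

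With 20% affected and HR 1.25, the powers are about 4 to 6%, 73 to 78% and 94%. The second row isolates the netting: harm and window are the same, and only efficacy differs.

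**Hand check of the third row.**

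- Symptom-free per arm: 300 × 0.40 = 120
- Control onset: 1 − 0.97^4 = 0.115
- IP onset: 0.115 + 0.885 × 0.15 = 0.248, a difference of 0.133
- Standard error: √(0.115×0.885/120 + 0.248×0.752/120) = 0.049
- z = 0.133/0.049 = 2.71, so power = Φ(2.71 − 1.96) = 0.77

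**If the IP also prevents new symptoms.** Cutting natural onset by 30% gives 1 − 0.979^4 = 0.081 natural onset on the IP and 0.081 + 0.919 × 0.15 = 0.219 in total. The difference is 0.104, the standard error 0.0477, z = 2.19 and power 0.59 (57 to 60% by simulation). A 50% cut gives about 45%. If 90% have the symptom at day 0, only 30 per arm remain and power is roughly 30%.

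**The case against.** The strongest reply has four parts.

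- **Detail.** Section 10 sends full statistical detail to the master SAP, and section 9 sends product-specific safety monitoring to the intervention appendices. Window and population for a symptom comparison usually belong there. This stands as a limit on weight. But the protocol itself names a comparison and its purpose, and for shared symptoms that comparison does not serve the purpose well.
- **No pooled score.** A reader might infer that the plan compares an overall symptom score. It does not. Symptoms are rated individually and over time, so the netting arises within each shared symptom. A look at daily trends during dosing could still show an excess.
- **Other routes.** A reader might infer that this comparison is the only way to detect drug-caused symptoms. It is not. AEs come from the diary and the day-14 call, are assessed by a clinician for causality and summarised by arm, and an unblinded safety board reviews safety data. These routes stand, but for overlapping symptoms they depend on attribution.
- **The alternative is not clean.** An effective product may also prevent new symptoms, which shrinks the new-onset contrast. Worsening above day 0 is likewise net of benefit, and someone already severe cannot worsen on a four-level scale. This is correct, and it is why the addition should not replace the trend comparison.

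The 1% power over 28 days is also tempting as a headline. Much of that weakness is dilution of a 7-day effect over 28 days, since power is only 28% even with no efficacy. The protocol does not specify a 28-day average either.

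**Conclusion.** The concern holds in limited form. For symptoms shared with the illness, the per-symptom between-arm comparison in 9.2.1 estimates harm net of any faster recovery. For an effective IP it can understate drug-caused symptoms, and under some assumed inputs it masks them fully: a daily drug-caused probability of about 3% to 16% at HR 1.2 to 1.5. In the simulated setting the days 1-7 contrast loses about half its power (77% to 39%) yet stays positive, so it would be too strong to say that harm and benefit generally cancel. AE recording covers the gap only in part.

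All sizes rest on assumed inputs. The documents also do not show that the trial will lack a better analysis, because the master SAP and intervention appendices are not at hand and may refine it. This is a cheap improvement of modest weight.

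**What to change.** Keep the trend comparison in 9.2.1 and add to that section, in substance:

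- For each solicited symptom, arms will be compared on new onset during the product-use days in the Symptom Free Analysis Set of section 10.6. The same days from randomisation are counted in the comparator.
- As supportive evidence, arms will be compared on worsening above the participant's own day-0 severity, over the same days, in the Symptomatic Analysis Set.

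The sets are defined by baseline status, so the comparison stays between randomised groups.

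The cost is wording in the protocol, mirrored in the master SAP. No new data are needed, because section 8.3 and its Table 1 already collect day-0 and daily symptom severity and daily product intake. The text should state the downsides: fewer participants per symptom, especially for symptoms that most people have at day 0; attenuation if the IP also prevents new symptoms; and a ceiling for those already severe at day 0. If the master SAP or an intervention appendix already contains such an analysis, a cross-reference from 9.2.1 is enough.
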